1.4 Prognostic factors for non-benign meningioma

1.4.1 Atypical vs. malignant meningioma

Because of the rarity of this disease, recognized prognostic factors are not available for grade WHO 2 and 3 meningiomas. It is usually admitted that the WHO histological grade (3 vs. 2) is associated with an adverse outcome. Palma *et al.* reported on the long-term prognosis of 71 atypical and malignant meningioma patients treated with surgery only (Ref. 2). The two groups were compared with respect to overall- and recurrence-free survival and median time to recurrence. The 10-year overall survival was significantly better for patients with atypical (79%) when compared to malignant (34.5%) tumors. Similarly, the recurrence-free survival and median time to recurrence (5 vs. 2 years) were significantly longer in patients with atypical than with malignant meningiomas. In the two published non-benign meningioma SRS series, a significantly improved clinical outcome was observed for atypical compared to malignant meningiomas (Ref. 21, Ref. 58). In the Princess Margaret Hospital series, a trend for an improved 5-year cancer-specific survival (CSS) was observed for atypical histology when compared to malignant histology (51% vs. 27%, univariate analysis $p=0.09$) (Ref. 32). The difference was however not significant in multivariate analysis. Hug *et al.* however reported an identical 8-year local tumor control rate (19% vs. 17%) for grade WHO 2 and 3 tumors. Likewise, Coke *et al.* did not observe a detrimental effect of histological malignancy on survival. Ten-year overall survival was 58% and 60% for grade WHO 2 and 3 meningioma, respectively (Ref. 30). These conflicting results illustrate how heterogeneous these retrospective studies likely are with respect to tumor histology. No clear definitions of the grading or of the resection completeness are clearly given in these series.

1.4.2 Extent of resection

Similarly to benign meningiomas, sub-total resection of malignant meningioma is associated with a significantly increased recurrence rate compared to total resection (Ref. 26). In the Baylor College series, the risk ratio for recurrence was 2.71 ($p=0.014$) when Simpson 1-3 were compared to Simpson 4 or more tumors (Ref. 25). Likewise, in the Goyal *et al.* series (Ref. 24) the 10-year overall survival was higher in patients with atypical tumors who underwent gross total resection (87%) than in those who did not have total excision (75%). Although this difference was not statistically significant for survival, it was for local control (87% vs. 17%, $p=0.02$). Similarly, Palma *et al.* observed that a Simpson Grade 1 resection for atypical or anaplastic leads to improved survival times (Ref. 2). Once recurrence develops, prognosis is poor as a result of the high likelihood of treatment failure (Ref. 25, Ref. 31).

1.4.3 Age

It has been shown that age less than 58 years was a significant predictor of 5-year CSS on multivariate analysis for both atypical and malignant meningioma (Ref. 32). This prognostic factor has not been assessed by other authors (Ref. 2, Ref. 24, Ref. 25, Ref. 30, Ref. 59).

1.4.4 Gender

It was suggested that male gender is associated with an increased risk of tumor recurrence in meningioma, possibly as a result of the association of male gender with high-grade (atypical/brain invasive) tumors (Ref. 16). For non-benign histology, gender was not significantly prognostic for survival and local control (Ref. 24). This factor has not been assessed by other authors (Ref. 2, Ref. 25, Ref. 30, Ref. 32, Ref. 59).

1.4.5 Pathology

Molecular prognostic markers have been described in benign and non-benign meningiomas. Perry *et al.* reported on 117 archival meningioma samples (benign, 42 cases; atypical, 52 and anaplastic, 23 cases) and determined the CDKNA (p16) deletion status (Ref. 80). This inactivation of the cell-cycle regulator, located on chromosome 9, has been observed in some atypical and the majority of anaplastic meningiomas. The CDKNA deletion was significantly associated with a shorter survival in the anaplastic meningioma cohort, with a risk ratio for death of 6.79. Conversely, the absence of this deletion identified a subset of anaplastic meningioma patients with a prolonged survival. It has been shown that a high MIB-1 labeling index may be associated with a poor prognosis. The same group evaluated primary GTR meningiomas from 425 patients with DNA flow cytometry, immunostaining for MIB-1, and determination of p53 protein expression (Ref. 81). Although p53 status was not associated with clinical outcome, an elevated MIB-1 labeling index of $\geq 4.2\%$, identified in 8% of cases, was strongly associated with decreased relapse-free survival in univariate analysis ($p=0.0001$). Caution should be taken when using the MIB-1 labeling index since substantial overlap exists for benign, atypical and anaplastic meningiomas (Ref. 82). Some series did not find a correlation between MIB-1 labeling indexes and clinical outcome (Ref. 83, Ref. 84).

Chromosomal and genetic aberrations differ with meningioma subtypes. Allelic loss at chromosome 22q is found roughly in 50% of WHO grade 1 meningiomas (Ref. 85). Allelic loss at additional chromosomal loci is associated with atypia and anaplasia in meningiomas. Lee *et al.* reported on 43 benign and non-benign meningiomas. The mean number of alleles with loss of heterozygosity (LOH) was 1.5 +/- 1.2 for benign meningiomas, 6.7 +/- 2.7 for atypical meningiomas, and 8.3 +/- 2.3 for anaplastic meningiomas ($p < 0.001$) (Ref. 86). Likewise, the Pitié-Salpêtrière group reported on 51 benign and non-benign meningiomas. LOHs on chromosomes 1p, 9p, 10q, 14q, and 22q, a deletion of CDKN2A, and telomerase activity was assessed (Ref. 87). LOH on chromosomes 22q, 1p, and 10q, as well as telomerase activity were significantly related to the WHO histological

grades of the lesions. Moreover, the LOH on chromosome 1p, 9p, or 10q; and telomerase activity, as well as histological and Simpson grade; were significantly correlated with a shorter PFS time. It thus seems that genetic changes are associated with meningioma progression (Ref. 88) but these genetic abnormalities have not been studied on prospective-collected pathology material. The EORTC planned study for benign meningiomas (26021/22021) and this study (atypical and malignant meningiomas) gives a unique opportunity to undertake a number of translational research projects on prospectively collected tumoral tissues (paraffin block and frozen material).

In summary, it is unclear if the clinical outcome of patients with grade WHO 3 tumors is significantly worse than that of grade WHO 2 meningiomas. Clinical characteristics (age, gender) do not seem to have a major impact on outcome for non-benign meningioma patients. The absence of total gross resection (Simpson 1-3) apparently negates the overall prognosis of grade 2 and 3 meningioma patients, alike. Because of the possible influence of the extent of resection on the clinical outcome, it was decided to stratify for resection and administer a higher dose to patients with subtotal resection. Atypical (grade WHO 2) tumors will be eligible for this study. Malignant meningioma is a rare disease, accounting only for 1-2% of all meningiomas. It is thus questionable if a prospective phase II study could be carried out with a sufficient number of eligible patients. Despite the unknown significance of a WHO grade 3 in meningiomas, it is of importance to prospectively assess the outcome of these rare tumors. As such, malignant (grade WHO 3) will be registered in the present study, with no dose escalation (i.e. 60 Gy to the tumor bed).

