
Treatment
 
Test product, dose and mode of administration
	
The treatment dose will be determined in function of the Simpson's stage.
 
Irrespective of WHO tumor grade patients with Simpson stage 1-3 will receive 60 Gy to the CTV1 and those with Simpson stage 4-5 will be treated with 60 Gy to CTV1 followed by a 10 Gy boost to the CTV2 (total, 70 Gy).
 
Volumes and prescribed dose should be according to the ICRU-50 report.
 
 ◆ GTV: postoperative tumor residual (CT or MRI). ◆ CTV1: GTV and/or subclinical microscopic tumor (may include the pre-operative tumor bed, peritumoral edema, hyperostotic changes if any, and dural enhancement or thickening as seen in the CT/MRI at diagnosis) + 10 mm or less, see dose constraints below. ◆ CTV2: GTV + 5 mm margin or less (see dose constraints, below). ◆ PTV1 & PTV2: CTV1 & CTV2 + 5mm margin (3 mm for stereotactic irradiation). These volumes needed to cover the CTV1 & CTV2 with the 95% isodose line, respectively. 
Fractionation: 2 Gy daily fractions, 5 fractions a week
 
Radiation quality: photon (> 4 MV) beams either conformal, stereotactic, or intensity-modulated radiation therapy (IMRT).
 
Dose constraints (total dose):
 
 ◆ optic pathways: 56 Gy (average); 60 Gy (maximum). ◆ Pituitary gland: 56 Gy. ◆ Brainstem: central, 54 Gy; surface, 64 Gy.
Duration of treatment	The treatment duration is therefore 6 weeks for Simpson's stage 1-3 and 7 weeks for Simpson's stage 4-5.
Reference therapy, dose and mode of administration	Not applicable

Criteria for evaluation
 
Efficacy
 
Safety
	
The primary trial endpoint is the 3-year progression-free survival rate in each stratum of the phase II study.
 
Progression-free survival is counted from entry on study until the first event of either death or progression (as demonstrated by an MRI showing either appearance of new lesions or increased in tumor size by 25% using 3 dimensions)
 
Overall survival is a secondary endpoint and is measured from date of entry to date of death, irrespective of the cause.
 
For both endpoints, the patients not having experienced the event(s) of interest are censored at the date of most recent follow-up.
 
Acute and long term toxicity will be scored according to the NCI-CTCAE version 3.0.
 
Neurological function will be measured by the Mini-Mental Status Evaluation.

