1.7 Conclusions

The overall policy in the treatment of non-benign meningiomas is controversial. It usually includes aggressive surgical resection of the tumor and of its dural attachments. If complete resection of the tumor is not possible or if it is deemed to be associated with an unacceptable morbidity, surgery should be more reserved. Post-operative radiation might reduce the local tumor recurrence rate for these aggressive tumors. A dose-response relationship has been suggested by several retrospective studies although this issue is controversial. Considering the lack of prospective data and the controversy around the dose escalation issue for this tumor entity, it was decided to perform the present prospective phase II study. There is no prospective study addressing the potential local control benefit of adjuvant high-dose radiotherapy for non-benign meningiomas weighted against the potential radiation induced toxicity. Atypical (grade WHO 2) patients will be accrued in this study. A separate observation study will be initiated for malignant (grade WHO 3) meningiomas, as this tumor type is rare (see Prognostic factors in meningiomas, section 4.1.5). No dose-escalation policy is planned for malignant meningiomas.

2 Objectives of the trial

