5.1.5 Target dose

Prescription point: Dose prescription for the PTV will be at or near the centre of this volume following recommendations of ICRU 50/62 reports (Ref. 89).

Dose definition: The absorbed dose is specified as Gy.

Tissue heterogeneity: Inhomogeneity correction for bone and soft tissue density variation will be applied.

Prescribed dose and fractionation:

- ◆ The prescribed dose for the CTV is 60 Gy in 30 fractions (Simpson's stages 1-3) or 70 Gy in 35 daily fractions (Simpson's stages 4-5) in one course.
- ◆ Fraction size is 2Gy

- ◆ One fraction given per day, five fractions per week so that overall treatment duration should be 6-7 weeks
- ◆ Dose specification and homogeneity requirements in the PTV (-5% $+7\%$) have to be in accordance with the ICRU guidelines.
- ◆ Interruptions: Patients requiring an interruption in radiotherapy will not receive additional fractions in order to compensate for potential tumor cell repopulation during the treatment gap. (hyperfractionation is not allowed).

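### For grade III patients with Simpson stage 4-5 resection, the protocol's chapter 1 rules out dose escalation (60 Gy) while its summary and section 5.1.5 lead to 70 Gy

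*Protocol*

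**What the plan says.** **Chapter 1.** The closing summary of section 1.4 (printed at the end of 1.4.5) says of grade III: "malignant (grade WHO 3) will be registered in the present study, with no dose escalation (i.e. 60 Gy to the tumor bed". Section 1.7 adds: "No dose-escalation policy is planned for malignant meningiomas". Neither sentence separates Simpson stage 1-3 from stage 4-5. Section 1.7 names no dose.

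**Protocol summary, Treatment.** Dose depends on resection stage alone: "Irrespective of WHO tumor grade patients with Simpson stage 1-3 will receive 60 Gy to the CTV1", while "those with Simpson stage 4-5 will be treated with 60 Gy to CTV1 followed by a 10 Gy boost to the CTV2 (total, 70 Gy").

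**Section 5.1.5.** "The prescribed dose for the CTV is 60 Gy in 30 fractions (Simpson's stages 1-3) or 70 Gy in 35 daily fractions", the latter for Simpson stages 4-5. WHO grade is not mentioned.

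**Chapter 4.** Grade III patients are to be treated, and then followed, in a similar way to grade II patients.

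**Section 8.1.2.** Grade III with Simpson stage 4-5 is one of the four groups formed at registration, so the affected patients are a foreseen part of the trial.

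**The concern.** A radiation oncologist with a grade III, stage 4-5 patient finds one sentence about this study's grade III patients that rules out escalation and names 60 Gy. The same reader finds a treatment rule that gives 70 Gy. Both cannot apply to the same patient.

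First at stake is the treatment itself. Section 1.6.2 urges great care with high-dose radiotherapy, and here the dose level is what is unclear.

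The second consequence concerns interpretation. If centres resolve the conflict differently, dose within grade III stage 4-5 would depend on the centre. Sections 8.2.3.1 and 8.2.3.3 tabulate adverse events separately for this group, and section 8.2.3.1 pools grade III efficacy over Simpson stage. Both results would then carry a dose variation that nobody planned.

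**Working it through.** **1. Are the stated doses internally sound?** Section 5.1.5 gives the fraction size: "Fraction size is 2Gy".

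- Simpson 1-3: 30 fractions × 2 Gy = 60 Gy.
- Simpson 4-5: 35 fractions × 2 Gy = 70 Gy.
- Protocol summary, Simpson 4-5: 60 Gy + 10 Gy boost = 70 Gy.

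The summary and section 5.1.5 agree, so the conflict is not an arithmetic slip.

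**2. Grade III dose by source.**

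| Source | Grade III, Simpson 1-3 | Grade III, Simpson 4-5 |
|---|---|---|
| End of section 1.4 | 60 Gy | 60 Gy, no escalation |
| Section 1.7 | no escalation, dose not given | no escalation, dose not given |
| Protocol summary | 60 Gy | 70 Gy |
| Section 5.1.5 (grade not mentioned) | 60 Gy | 70 Gy |
| Chapter 4 | as grade II | as grade II |

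The sources that give a dose agree on the first column and disagree on the second.

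**3. Size of the disagreement.** 70 − 60 = 10 Gy. At 2 Gy per fraction, 10 / 2 = 5 fractions. At five fractions a week this is one week, matching the 6 and 7 weeks in the summary.

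**4. How many patients?** The protocol expects 6-13 grade III patients over all Simpson stages and gives no split by stage. The number in stage 4-5 could be anything from none to all of them.

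**5. Can the sentences be read together?** One could take 60 Gy to the tumour bed as the first phase only, with a boost to follow. But the same sentence rules out escalation for grade III, and section 1.7 repeats this. The preceding text in section 1.4 is itself mixed: it describes poorer prognosis after incomplete resection in grades 2 and 3 alike, then a higher dose after subtotal resection, then the grade III statement. The term is not used consistently either. Section 2.1 counts both 60 and 70 Gy as dose escalation, whereas section 1.4 equates 60 Gy with none.

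**6. What is untouched?** The primary endpoint and both sample sizes (25 and 39) concern grade II only. As a side check with exact binomial counts, at least 21 of 25 successes gives α = 0.0905 and β = 0.0980. At least 24 of 39 gives α = 0.0998 and β = 0.0944. These match the stated 0.09/0.098 and 0.10/0.094. No grade III patient enters either calculation.

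**The case against.** The strongest reply is that chapter 1 is background and chapter 5 governs. Section 5.1.5 gives one prescription by Simpson stage, the summary expressly addresses grade, and chapter 4 points the same way. The quality assurance programme in section 15.4 collects each patient's prescription, gives each centre's first case a timely review and then reviews every case. A divergent dose would be visible.

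Much of this stands. The treatment chapter does not contradict itself, and it would be too strong to say that quality assurance has no reference.

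It does not remove the conflict. The two chapter 1 sentences do not report literature; they say what this study will do with grade III patients. The text available states no order of precedence. Section 5.1.5 is silent on grade, so in the protocol body the only explicit grade III dose is the one at the end of section 1.4, which a reader could take as a deliberate exception. Chapter 4 does not fully settle it either: the parallel sentence in section 8.1.1 speaks only of similar follow-up, and section 1.7 calls the grade III part a separate observation study.

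**Conclusion.** The contradiction is real and lies in current text. For grade III with Simpson stage 4-5, following the protocol leads to two prescriptions 10 Gy apart. It should be corrected because it concerns a prescribed radiation dose and is cheap to resolve. The conclusion rests on the wording alone and on the absence of a precedence rule in the text available. It takes no position on which dose is right.

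Some stronger inferences are not supported:

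- **That section 1.7 also prescribes 60 Gy.** It gives no dose; only the end of section 1.4 does.
- **That the conflict spoils the only grade III result.** Pooling over stage applies to efficacy. Adverse events and the MMSE normal/impaired proportions are shown for grade III by Simpson stage.
- **That the conflict alone puts mixed doses into the pooled efficacy estimate.** Under the summary and section 5.1.5, pooling stages 1-3 and 4-5 already combines 60 and 70 Gy. The added problem is centre-dependent variation within stage 4-5.
- **That a given percentage of grade III patients is affected.** Without a stage split, any percentage is an assumption.
- **That the trial's main conclusions are at risk.** Grade III has no decision rule or sample size and is reported descriptively.

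**What to change.** The sponsor must reconcile the Treatment entry of the protocol summary, the closing summary of section 1.4, section 1.7, chapter 4 and section 5.1.5. The prescription should then be stated once, by WHO grade and Simpson stage, in section 5.1.5, with the other places made to agree. Sites and the radiotherapy quality assurance team should be told, so that case review for this group uses the same reference. Which dose applies is for the sponsor and the clinical investigators to decide.

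The cost is a protocol clarification or amendment and a letter to sites. It needs no additional patients and no change to the statistical design.

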1.5 Target volumes

The definition of target volumes is essentially based on the ICRU 50/62 recommendations (Ref. 89). Target definition with respect to meningioma margins has not been prospectively addressed in the literature. Although the atypical (grade WHO 2) meningiomas do not infiltrate normal brain, adjacent bone structures and dura can be involved. Not infrequently, perivascular extension along the Virchow-Robin spaces happens. Therefore both CT and MRI are mandatory diagnostic techniques to delineate visible tumor and form the starting point for target volume definition (Ref. 71) (see Rational of adjuvant radiotherapy, chapter 1.3). Substantial differences and uncertainties exist, however, in a consistent delineation of macroscopic disease between both techniques. Khoo et al. reported on 7 skull base meningioma patients imaged with CT and MRI. In this series, MRI appeared to define target volumes that were larger but not inclusive of those defined by CT (Ref. 90). For the delineation of the gross tumor volume (GTV) for treatment planning it is therefore necessary to pragmatically define the tumor extension with maximum information by using both techniques. The high dose delivery in this study requires an optimal precision of treatment delivery, which demands in turn a greater accuracy of tumor delineation to avoid marginal target misses.

Although no reliable data exist, when applying fractionated irradiation, most radiation oncologists consider that sub clinical disease (i.e. Clinical Target Volume, CTV) need to be anticipated approximately 1 cm beyond dural thickening. This is not the case in normal brain and bony structures unless frank brain or bone invasion is documented. In order to limit the radiation induced toxicity after high dose radiotherapy for macroscopic disease (see Toxicity, chapter 1.6), it is necessary to tighten the margins around the GTV. CTV will be defined by adding 1 cm (CTV1) and 0.5 cm (CTV2) during the first part of the irradiation and cone-down, respectively. Various studies have shown undisputedly that rigid face masks or stereotactic relocable frames offer a high level of geometric accuracy.

Kortmann et al. reported on a quantitative assessment of the accuracy of field alignments in 95 patients presenting with difficult positioning (Ref. 91). In this series, conventional radiotherapy (2D) was administered. The observed precision (standard deviation) was 2.5 mm, with patient immobilization using a thermoplastic face mask. The same group reported on the geometric accuracy of SRT in 20 brain tumors patients (Ref. 92). SRT was administered with a stereotactic

target positioning device. Ninety-five % of all absolute deviations were between less than 4.6 mm. The Royal Marsden group have shown that a precision of 1 mm could be achieved using a Gill-Thomas-Cosman frame (Ref. 93). As such, a 5 and 3 mm setup precision will be assumed for 3D CRT and SRT, respectively. These margins can however be tightened, depending on departments' policy to define the institutional safety margin with respect to their radiation therapy techniques.

1.6 Toxicity

1.6.1 Radiation-induced toxicity with conventional dose fractionated radiotherapy

Radiation-induced toxicity after radiotherapy is infrequent and range between 2% (Ref. 94) and 30% (Ref. 63). Radio surgery probably induced more treatment related morbidity (Ref. 95) when compared to fractionated radiotherapy (Ref. 75, Ref. 76). In two large series of patients with benign meningiomas, significant long-term toxicity was reported in 2% (Ref. 94) and 4% (Ref. 41), respectively. The dose to the tumor dose ranged from 50 to 55 Gy in the first study (Ref. 94), in which 50% of the tumor were in the more favourable para-sagittal or cortical location, and the median target dose was 54 Gy in the second study (Ref. 41). These data indicates that radiation-induced morbidity is unusual but possible even with 'standard' dose radiotherapy.

1.6.2 Radiation-induced toxicity with high-dose fractionated radiotherapy

Among other factors, such as tumor location and irradiated volume, the complication rate is closely related to the administered dose. As mentioned earlier (see Rational of adjuvant radiotherapy, chapter 1.3), patients with non-benign meningiomas have been treated at a higher dose. Only one of these these series reported unusual treatment-related toxicity (Ref. 2, Ref. 24, Ref. 25, Ref. 30, Ref. 31, Ref. 32). Katz et al. reported on 36 patients (atypical, 27 patients; malignant 9 patients) treated with an aggressive radiotherapy schedule consisting of 60 Gy (at 1.5 Gy per fraction twice daily), with or without a radio surgery boost (median dose, 12.5 Gy) (Ref. 59). This radiation regimen was chosen because it appeared well tolerated in GBM (Ref. 96). A shrinking field technique was used in most cases. One third of the patients developed a severe complication: 6 patients presented with a grade NCI-RTOG 3 and 4, respectively. No grade 5 complication (i.e. death attributed to treatment) was observed. The majority (10/11) of these patients presented clinically with persistent radio-necrosis (median time of steroids administration, 1 year). The complication rate for those treated with accelerated hyperfractionated radiotherapy was significantly higher (grade 3, 0% vs. 55%; grade 4, 0% vs. 27% for non- and accelerated hyperfractionated radiotherapy, respectively). It is likely that the radiation-induced toxicity could not be optimally assessed in these retrospective series, excluding the University of Florida data (Ref. 59). As a result, all high-dose radiotherapy published data focus on tumor control and complication rates are scarce. Identically, the Boston group reported a high complication rate after combined photon and proton radiotherapy (median dose, 59 Gy; range, 53.1 – 74.1) for benign meningiomas in their prospective series (Ref. 61). The 10-year survival without significant grade 3-4 morbidity was 80%. As a result of the observed toxicity, the optic structures-dose constraints were substantially modified (from \leq 62 Gy to 54 Gy) during accruing period.

All these data undisputedly show that great care should be advised in delivering high-dose radiotherapy to those patients. Strict dose constraints (see Normal tissue sparing, chapter 5.1.7) should be implemented and the target volume should be precisely defined (see Target volume definitions, chapter 5.1.2) in order to avoid significant radiation-induced toxicities.

